### ***Adoptability***

Adoption refers to the uptake of Baby Bridge programming, measured at the organizational and provider level (Proctor et al., 2011). This can include health care professionals' buy-in and support of the program that enables infants and families to receive Baby Bridge services. We tracked the number of infants referred, approached, and enrolled. Adoption was operationalized to include the total number of infants approached versus enrolled (enrollment rate).

### ***Feasibility***

Feasibility is defined as the extent to which Baby Bridge programming can be successfully used or carried out within a given agency or setting (Proctor et al., 2011). To understand the feasibility of Baby Bridge telehealth programming, we captured timing (if the first visit was conducted within one week of discharge); average time from NICU discharge to first Baby Bridge visit); frequency of visits; rate and reasons for any therapy visit cancellations; the completion rates (percentage of enrolled infants who completed programming); and the timing of transition to community-based therapy. Feasibility was defined a priori as all Baby Bridge visits attempted within the first week, infants seen at least 3 visits per month while in the program, and that 80% would be successfully transitioned to early intervention programming.

### ***Adaptations***

Adaptations include intentional changes made to programming (from the way it was intended) in order to enable real-world uptake by aligning the intervention to the context it exists in (Moore et al., 2021). To aid in understanding specific adaptations made to telehealth versus in-person programming, we captured the proportion of visits conducted via telehealth in the telehealth group and proportion of visits that occurred in-person in the in-person group. Reasoning for such adaptations was tracked as described above in the telehealth and in-person assignment sections.

### ***Acceptability***

Acceptability is the perception among stakeholders, specifically the consumers or parents, that the Baby Bridge program is satisfactory. Using Proctor's model (Proctor et al., 2011) as a guide and through adaptation of a previously reported measure of acceptability (Karlsson & Bendtsen, 2005), the Baby Bridge Parent Survey was developed to determine if programming was acceptable to parents. The survey was developed, and five members of the research team added/revised queries to aid in comprehensive collection of perceptions as well as to aid clarity of each question's wording. It went through an iterative process with multiple revisions until no further feedback from team members was received and there was consensus on the inclusion of and the wording of survey questions. The survey took < 5 minutes to complete.

Upon completion of the Baby Bridge program, parents were asked to complete the Baby Bridge Parent Survey to query their perceptions about Baby Bridge programming. Survey questions were loaded into REDCap and administered electronically through a shared link to a REDCap survey. Parents received subject remuneration of \$50 after completing the survey. Parent satisfaction was measured based on a sum (possible range of 0-10) of the following questions from the survey:

1. Were therapy goals achieved through Baby Bridge programming (2=yes, 1=partially, 0=no)
2. How likely would you be to recommend the Baby Bridge program to other NICU parents? (3=definitely will, 2=probably will, 1=probably will not, 0=definitely will not)

3. How likely would you be to use Baby Bridge programming again? (3=definitely will, 2=probably will, 1=probably will not, 0=definitely will not)
4. Was there anything about the Baby Bridge program that you found confusing or complicated? (0=yes, 1=no)
5. Did you experience any challenges with the Baby Bridge program (0=yes, 1=no).

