## Study Protocol and Statistical Analysis Plan

### **Participants and setting**

Participants included 20 high-risk parent-infant dyads hospitalized in an urban, level IV NICU. Consecutively eligible dyads from May 2023 to April 2024 were recruited if the infant was hospitalized in the NICU for > 7 days; received a referral for post-NICU physical therapy, occupational therapy, and/or speech-language pathology (or for the state-wide early intervention program) at NICU discharge; was referred to the Baby Bridge program at least 48 hours before NICU discharge; had a chronological age of < 6 months at the time of NICU discharge; and were from a family who spoke English. Infants who lived any distance away from the hospital were enrolled; however, infants who were not going to reside in the state of California following NICU discharge were excluded. Infants were deemed 'high-risk' for developmental challenges if they were recommended by the NICU medical team for therapy. Although we acknowledge that the term "high risk" can refer to high risk of medical complications or high risk of cerebral palsy, we use the term "high risk" to define the infant's need for therapeutic interventions across a multitude of constructs including for language, cognition, self-regulation, sensory, motor, and feeding. A member of the research team attended weekly discharge rounds and reviewed the electronic medical record. Within discharge rounds, communication between the medical team and research team occurred, and the medical team referred infants to the Baby Bridge program through an online referral process in REDCap. The research team then screened and recruited those who were eligible.

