Enrolled infants and families were randomized to receive Baby Bridge services either through telehealth or in-person visits. Parent-infant dyads were enrolled at least 2 days before NICU discharge to enable rapport to be established (between the Baby Bridge therapist and family) through a visit to the NICU when possible and via telephone, text or email messaging when an in-person visit was not possible prior to discharge. This first contact was attempted to be in-person in the NICU for both the telehealth and in-person groups. Enrolled infants and families then had a Baby Bridge telehealth or in-person visit scheduled within one week of discharge (depending on their group assignment). Subsequent individual weekly visits were adapted to in-person or telehealth (varying from assigned group) when needed or deemed appropriate (requested by the family or therapist or when an in-person visit was felt to improve the quality of the therapy session). Weekly Baby Bridge programming was conducted until other therapy through the state-wide early intervention program commenced, as in the infant was receiving therapy services as recommended. We also tracked rates of enrollment, rates and reasons for any cancellations, and completion of the program (defined as being seen until community-based early intervention services commenced). Infants were withdrawn if they were transferred to another hospital or if they were readmitted to the hospital and additional contact was not possible or feasible.

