## **Feasibility**

We investigated differences across groups (in-person versus telehealth) in whether the first visit occurred within 1 week of NICU discharge, average number of days between NICU discharge until first Baby Bridge visit, frequency of visits, number of therapy visit cancellations, and the completion rates using independent samples t-tests and chi-square analysis.

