### ***Acceptability***

Satisfaction scores were compared across groups using independent samples t-tests.

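### The satisfaction survey is triggered only by programme completion, so as written the acceptability comparison leaves out randomised families who did not complete

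*Combined protocol and SAP*

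**What the plan says.** All references are to the combined protocol and SAP.

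- **Survey timing** (Acceptability, under Implementation outcomes): "Upon completion of the Baby Bridge program, parents were asked to complete the Baby Bridge Parent Survey". No other time point or trigger appears. The survey is a REDCap link taking under 5 minutes, with $50 paid on completing it. Five items are summed to a score from 0 to 10.
- **Meaning of completion** (Participants and setting): "completion of the program (defined as being seen until community-based early intervention services commenced".
- **Withdrawal** (Participants and setting): "Infants were withdrawn if they were transferred to another hospital or if they were readmitted to the hospital", the readmission route applying where further contact could not be had.
- **Completion as an outcome** (Feasibility, under Implementation outcomes): "the completion rates (percentage of enrolled infants who completed programming". The same section sets a benchmark that "80% would be successfully transitioned to early intervention programming". The Feasibility part of the Analysis section then compares between arms "the completion rates using independent samples t-tests and chi-square analysis".
- **Acceptability analysis** (Analysis section): "Satisfaction scores were compared across groups using independent samples t-tests". This one sentence is the whole plan. It gives no analysis set, response count or rule for missing scores.

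**The concern.** Because completion is defined, the survey trigger does not naturally read as the end of participation for any reason. A family whose infant was not seen until early intervention began is a non-completer, and the plan gives that family no route to the survey. The satisfaction t-test is then conditioned on something that happens after randomisation, and which the plan itself treats as able to differ between arms.

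Two results are exposed. The acceptability mean may describe completers and not all randomised families, although acceptability is defined in terms of parents generally. The arm comparison loses the protection of randomisation if completion, or the satisfaction of non-completers, differs by arm. The Analysis section says the pilot is meant to show initial group differences and to supply variances for a larger trial, and a completer-only sample could affect both.

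Reporting completion rates shows part of the possible selection. It does not show who answered the survey or how far the score could move.

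**Working it through.** **Inputs from the documents.** There are 20 dyads (Participants and setting), a score range of 0 to 10 (Acceptability) and a transition benchmark of 80% (Feasibility).

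**Assumptions.** The allocation ratio is not stated, so 10 per arm is assumed. The completer mean of 9 is assumed. The 80% is borrowed as a completion rate; it is a target for transition, not a forecast of completion or survey response.

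**Reproducing the plan's own figure.** The item maxima sum to 2 + 3 + 3 + 1 + 1 = 10 and the minima to 0, which matches the stated range. There is no sample-size calculation to reproduce.

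**Bounds on the overall mean.** At the benchmark, 0.80 × 20 = 16 families are surveyed and 4 are not. Filling the missing scores with 0 or 10:

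- low: (16 × 9 + 4 × 0)/20 = 7.2
- high: (16 × 9 + 4 × 10)/20 = 9.2

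The width is 10 × (share not surveyed), whatever the completer mean. Each missing family therefore adds 10/20 = 0.5 points.

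| Surveyed | Width of bounds (points) |
|---|---|
| 20/20 | 0 |
| 18/20 | 1.0 |
| 16/20 | 2.0 |
| 14/20 | 3.0 |

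**Bounds on the arm difference** (both observed means 9):

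- 8/10 surveyed in each arm: each arm mean lies in (72 + 0)/10 = 7.2 to (72 + 20)/10 = 9.2, so the difference lies in −2.0 to +2.0.
- 9/10 in each arm: each arm mean lies in 81/10 = 8.1 to (81 + 10)/10 = 9.1, so the difference lies in −1.0 to +1.0.

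**Less extreme illustration.** Let q be the non-completer share and d the completer mean minus the non-completer mean. The completer mean exceeds the all-randomised mean by q × d. With q = 0.2, this is 0.2, 0.4, 0.6 or 1.0 points for assumed d = 1, 2, 3 or 5. If d were negative, the error would run the other way.

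For the arm difference, with d equal in both arms, the bias is (q₂ − q₁) × d. With four non-completers in total:

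| Non-completers by arm | q₂ − q₁ | Bias for d = 1 to 5 (points) |
|---|---|---|
| 2 and 2 | 0 | 0 |
| 1 and 3 | 0.2 | 0.2 to 1.0 |
| 0 and 4 | 0.4 | 0.4 to 2.0 |

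The bias is also zero if d = 0, that is, if non-completers would have scored the same as completers.

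**The case against.** The strongest reply is that the plan says when parents were asked, not that anyone was refused. No selection is demonstrated: the documents do not report how many families failed to complete, and if all completed and responded there is nothing to correct. The withdrawal routes described are medical or logistical and are not signs of dissatisfaction. Families lost after readmission are, by the plan's own condition, those who could not be reached, so a wider survey would recover few of them. The bounds would arise with any missing data on a 0 to 10 scale. The a priori success criteria concern feasibility, and no decision depends on the satisfaction score; cost is the primary outcome of an unpowered pilot. Item 1, on goals achieved, presumes some exposure to the programme. Finally, recruitment ended in April 2024 and the text is in the past tense, so new surveys may be impossible.

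Much of this stands as a limit on size and priority. The amount of bias is unknown and may be zero, the bounds are mechanical, and the outcome is secondary. It does not remove the point. The only trigger given is a defined event that some randomised families may not reach, and nothing in the plan would let a reader see whether that happened among respondents. The no-contact condition is attached to readmission, so other non-completing families may be reachable. Limited exposure and closed data collection bear on the choice of remedy, and the fix below allows for both.

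**Conclusion.** The concern holds. As written, the satisfaction comparison covers families selected by programme completion after randomisation, with no stated analysis set and no planned account of survey response. The mean may not represent all randomised families, and the arm comparison may be biased if completion, or non-completers' satisfaction, differs by arm.

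Direction and size cannot be determined from the documents. With 16 of 20 surveyed, the all-randomised mean is left undetermined over 2.0 points. With 8/10 surveyed in each arm and equal observed means, the arm difference is left between −2.0 and +2.0. These figures rest on the borrowed 80% and the assumed 10 per arm; the widths do not depend on the assumed mean of 9. They are bounds, not estimates of bias, and they shrink to zero if every family was surveyed. This merits a change to a secondary outcome and leaves the primary cost comparison untouched.

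**What to change.** **If the survey is still open:**

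- Send the same REDCap link, with the same $50, to every enrolled parent who can be contacted when they leave the programme for any reason.
- Compare satisfaction by randomised arm.
- Report respondents out of randomised, by arm and completion status, with best- and worst-case bounds that set non-respondents to 10 and 0.
- Report the number of visits received alongside the score for families with little or no exposure, since item 1 means little for them.

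The cost is a few extra $50 payments. Some withdrawn families will not respond or will have seen little of the programme, and the mean score may change.

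**If data collection has closed:** label the result as satisfaction among completers, restrict the conclusion to them, and report the same counts and bounds. The cost is one table and a narrower conclusion.

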## **Analysis**

A power analysis to determine sample size was not conducted, as this is a pilot study aimed at understanding initial differences across groups while determining variance to aid in future sample size determination for a larger trial. Sociodemographic and medical factors are reported descriptively and differences across groups were investigated using independent samples t-tests and chi-square analysis.

## **Cost**

The cost of in-person visits vs. telehealth visits are reported descriptively. Differences in costs across telehealth and in-person visits were investigated using independent samples t-tests and linear regression models.

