### **Implementation outcomes**

We defined measures for this study based on previous implementation research (Lewis et al., 2015; Proctor et al., 2011; Proctor et al., 2009). The primary outcome of interest for this study was cost difference between telehealth and in-person visits of the Baby Bridge program. We also investigated implementation outcomes of adoptability, feasibility, adaptations, and acceptability. Many of the procedures here mirror a previous article on feasibility, which enrolled a different sample to assess the same outcomes in context of telehealth only, whereas this manuscript enables exploration of the differences when comparing to an in-person model.

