### **Cost**

Cost is an important factor when determining feasibility of an intervention. When resources are limited, it can aid in choosing one intervention over another. For the purposes of this project, we estimated costs associated with each Baby Bridge visit. We did not assess cost across group assignment, due to the allowed adaptations to each visit type. Cost was defined in relation to the organizational cost of providing Baby Bridge visits and included the time that the therapist spent conducting therapy sessions (billable time), administrative time (documentation, communication with families), driving (for in-person visits), and mileage reimbursement. The total billable and non-billable time that the therapist spent (including therapy session time, administrative time, and drive time) was

multiplied by \$50 per hour, an hourly wage that matches typical rates across the United States and in California (29-1122 *Occupational Therapists*, 2024). Mileage reimbursement was calculated at the \$.67 per mile, the California mileage reimbursement rate for employees (2024 *Updated Mileage Reimbursement Rates for Use of Personal Vehicle and Private Aircraf*, 2024). Further, the number of billable minutes (in evaluation, for therapeutic activities, or therapeutic exercises) were put in context of Current Procedural Terminology (CPT)/Healthcare Common Procedure Coding System (HCPCS) codes and reimbursement amounts for Fee For Service Medi-Cal (California Medicaid) (though we acknowledge this reimbursement rate could differ drastically depending on actual insurance type). This enabled a total amount of reimbursable potential in context of the total cost of programming, with the ability to explore differences across telehealth and in person costs. Because many infants had some adaptations to their assigned type of therapy visit, rather than investigating across assigned groups, we analyzed cost based on actual visit type (telehealth or in person) rather than assigned group type.

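### The primary cost comparison treats weekly visits to the same 20 dyads as independent, so its error bars are invalid and probably too narrow

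*Combined protocol and SAP*

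**What the plan says.** Implementation outcomes names the primary outcome: "The primary outcome of interest for this study was cost difference between telehealth and in-person visits of the Baby Bridge program". The Cost paragraph in that section sets the unit ("we estimated costs associated with each Baby Bridge visit") and compares by the type of visit actually delivered, not by randomised group, because "many infants had some adaptations to their assigned type of therapy visit". Besides session and administrative time, cost includes "driving (for in-person visits), and mileage reimbursement".

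Participants and setting gives the sampling structure: "Participants included 20 high-risk parent-infant dyads". On repetition it says: "Weekly Baby Bridge programming was conducted until other therapy through the state-wide early intervention program commenced". On distance it says: "Infants who lived any distance away from the hospital were enrolled"; the only geographic limit is residence in California.

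The Analysis section, under Cost, promises descriptive reporting and then the inference: "Differences in costs across telehealth and in-person visits were investigated using independent samples t-tests and linear regression models". The covariates and error structure of the regression are not described. Nowhere do the documents mention a dyad effect, a dyad-level summary, a paired analysis or a cluster-robust error.

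**The concern.** The rows in the primary analysis are visits, but the independent units are the 20 dyads. An independent-samples t-test assumes that every row is independent within and between the two visit types. Here each dyad contributes several rows, and a dyad that switched mode contributes to both sides. Ordinary regression on visit type rests on the same assumption.

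The cost definition suggests the direction of the error. Drive time and mileage for a given home are much the same each week, and they apply to one mode only. In-person visits to the same home should therefore be positively correlated, and mixing modes within a dyad does not cancel that.

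What is at stake is the precision claimed for the primary result. A second, conditional harm concerns planning. The Analysis section gives variance estimation for a larger trial as an aim of the pilot. If the cost variance is used to plan a trial that randomises dyads, a single visit-level SD is not enough, because it is not split into between-dyad and within-dyad parts. The documents do not say which outcome or design that variance would serve.

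**Working it through.** The plan gives no standard error, interval, alpha or power figure for cost, so there is nothing to reproduce. The check asks how far the naive error could be off.

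**Inputs from the documents:** 20 dyads; $50 per hour for all therapist time including driving; $0.67 per mile; travel cost on in-person visits only.

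**Assumed, because the documents are silent:** a 10:10 split, visits per dyad, home distances, driving speed, within-visit spread, intraclass correlation (ICC) and the share of visits in the assigned mode.

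**1. Dyad effect common to both modes.** With m visits per dyad and a share c of visits switched:

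DEFF = 1 + (m − 1) × (1 − 2c)² × ICC; true SE / naive SE = √DEFF; actual alpha = 2 × [1 − Φ(1.96/√DEFF)].

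- Example with m = 8, c = 0.1, ICC = 0.3: DEFF = 1 + 7 × 0.64 × 0.3 = 2.34; SE ratio = √2.34 = 1.53; actual alpha about 20% (19.8% by simulation).
- Range with m = 4 to 12, ICC 0.1 to 0.7, c = 0 to 0.25: DEFF 1.07 to 8.7, SE ratio 1.04 to 2.95, actual alpha 5.9% to 51%.
- Direction check: at c = 0.5, DEFF = 1. If every dyad had an exact half-and-half mix, the naive SE would be too wide, with ratio √(1 − ICC) = 0.95 to 0.55 for ICC 0.1 to 0.7.

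**2. Travel cost, in-person visits only.** The model was

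cost = $75 + N(0, SD $20) + [in-person] × 2 × distance × ($0.67 + $50/35).

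At an assumed 35 mph, each one-way mile adds 2 × (0.67 + 1.43) = $4.20 to an in-person visit. Distance was fixed per dyad and lognormal (median 10 or 20 miles, log-SD 0.2 or 0.7), with a mean of 4 or 8 visits and 50-100% of visits in the assigned mode. That makes 32 scenarios of 1,500 runs each. Coverage of the naive (Welch) 95% interval was:

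| Visits in assigned mode | Coverage |
|---|---|
| 50% | 60-92% |
| 70% | 59-93% |
| 85% | 49-92% |
| 100% | 45-92% |

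- Worst case (8 visits, median 20 miles, log-SD 0.7, no switching): mean reported SE $8.6, true SD $28.3, ratio 28.3/8.6 = 3.3, coverage 45%.
- Mildest case (4 visits, median 10 miles, log-SD 0.2, 70% in assigned mode): SE $4.7, true SD $5.0, ratio 1.1, coverage 93%.
- The naive test rejected in 100% of runs in all 32 scenarios.

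**3. Sensitivity.**

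- A second travel model (30 mph, 4 to 12 visits, median 10 or 15 miles, 0-50% switched) gave SE ratios of 1.19 to 3.47 and coverage of 42-90%. The ratio exceeded 1 in all 24 cases, including 50% switching. Pooled and Welch intervals were almost identical, so unequal variance is not the main cause.
- With half of the log-distance variance varying by trip instead of by home, naive coverage was 65-95%.

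**The case against.** The strongest reply is that nothing decisive depends on this. The study is an unpowered pilot, costs are first reported descriptively, and no threshold or go/no-go rule uses the test. The point estimate is not biased by clustering, and the test stayed significant in every travel scenario. All of that stands, and it limits the harm to precision. It does not make the error bars valid, and this is the only inference planned for the primary outcome.

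Other points against:

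- **No interval is promised.** True. The criticism applies to any standard error, p-value or interval these methods produce.
- **The regression might include a dyad term.** It is too loosely described to rule that out, but none is stated, and the t-test cannot contain one.
- **The lowest coverage assumes no switching, although many infants switched.** Fair. Restricting to 50-85% in the assigned mode still gives 49-93%.
- **A null of no cost difference is unrealistic, since in-person visits carry travel cost by definition.** Also fair, so the alpha figures matter less than coverage.
- **Switching may depend on distance.** The In-person group assignment section lists distance among the reasons for moving a visit to telehealth. When switching was made to rise with distance (strength assumed), naive coverage was 70-92% in one set of runs and 52-93% in another. The shortfall can be smaller but does not vanish. At log-SD 0.7 and a 20-mile median, such switching also moved the mean cost difference from about $107 to $86. Clustered errors do not address that shift.
- **The direction is not certain.** With a shared dyad effect and near-even mixing, the naive error could be about right or too wide. Hence 'probably'.

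**Conclusion.** The concern holds. The violation of independence follows directly from the text: per-visit costs, weekly visits, 20 dyads, and a test that ignores dyad. This is an error in the method as written, not merely missing detail. That the resulting interval is too narrow is probable, not certain. It rests on travel cost recurring by home and falling on one mode only, and on most visits following assignment.

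The size is conditional on the assumed ranges. Coverage could be close to nominal if distances are similar and visits few, or about half the nominal level if distances vary widely and visits are many. The sign of the cost difference is not in question, and a large travel-driven difference would probably stay significant after correction.

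**What to change.** In the Analysis section, under Cost, replace the visit-level t-test with a regression of per-visit cost on actual visit type. Use dyad-clustered standard errors with a small-sample correction for 20 clusters, for example CR2 with Satterthwaite degrees of freedom, and report the cost difference with that 95% interval. If home distance is included, enter it as an interaction with visit type, since it affects only in-person cost.

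Report the number of dyads contributing to each visit type and to both, the between-dyad and within-dyad variance components (by visit type if estimable), and the ICC.

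A mixed model with a random dyad intercept is an alternative. Add a dyad-varying visit-type effect only if it can be estimated: in 120 simulated fits each at 50%, 85% and 100% of visits in the assigned mode, that model failed 52, 50 and 83 times.

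The cost is a reanalysis of existing visit-level data and a reworded paragraph; no new data are needed. The intervals will be wider. With 20 dyads and skewed distances they can still fall somewhat short: the corrected interval covered 86-96% in simulation, with type I error of 4-7% under a shared-dyad-effect null.
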